## Promoting Follow-Up Care Self-Management for Adolescent and Young Adult (AYA) Childhood Cancer Survivors

[name], MPH

Treatment Evaluation Inventory-Short Form				
---	--	--	--	--

Mentors will be asked to complete a brief self-efficacy survey at time of training (Mentor Survey 1), a brief evaluation of the training (Mentor Training Evaluation), and a survey including program evaluation ratings when they have completed mentoring their last mentee (Mentor Survey 2). After completing the final call with each mentee, they will be asked to complete the Working Alliance Inventory – Short Form^41 regarding their relationship with the mentee.

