### **Aim 2: Evaluate the feasibility of the self-management + peer mentoring program.**

We will examine feasibility through study enrollment rates, retention rates, adherence to the intervention, reasons for study drop out, and patient and mentor satisfaction with the program.

*Hypothesis 1:* Based on literature, we expect enrollment >50% of eligible patients and retention >80%.

*Hypothesis 2:* We expect patients enrolled in the mentor program to complete >75% of intervention sessions

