#### ***3.1. Duration of Study***

Phase 1: Participants will be asked to complete a one-time interview lasting approximately 60 minutes.

Phase 2: Participants will be asked to complete the intervention over a period of 6 weeks. Participants will be asked to complete 6-week online self-management educational modules and 6 weekly peer mentor calls to facilitate engagement with the online modules and offer specialized support.

Phase 3A: Usability sessions will last approximately 1-hour. Given that usability testing is iterative and design changes are made in response to participant feedback, we will ask some participants if they are willing to review the product another time after changes are made, up to a total of five times. Each session is voluntary and conducted in a way to minimize participant burden.

Phase 3B: Participants assigned to the intervention will be asked to complete it over a period of approximately 8 weeks (which includes 6 peer mentor calls and five corresponding online modules). All participants will be asked to complete surveys at four time points: baseline, immediate post-intervention (~8 weeks after baseline), 3-month follow-up (~5 months after baseline), and 9-month follow-up (~12 months after baseline).

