**Table 1. Feasibility decision rules.**

Feasibility	Unacceptable Rate	Acceptable Rate	Decision rule for claiming Feasibility	Prob. Declare Feasible under Unacceptable Rates	Prob. Declare Feasible under Acceptable Rates
Acceptance	41%	50%	If 50 recruited by the 100th eligible	5%	97%
Retention	70%	80%	40 people complete	5%	94%

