**Promoting Follow-Up Care Self-Management for Adolescent and Young Adult (AYA) Childhood Cancer Survivors**

[name], MPH

Once the Medical Record Release form is completed, signed and returned along with the contact information of the doctors visited in the last 12 months, we will verify the contact information provided by the patient for completeness against publicly available data on the web. We will then mail, email, and/or fax the request for information to the doctor (depending on the contact information available) along with a cover letter and a copy of the signed medical record release form for the patient. We will follow-up with up to three phone calls or emails to the doctor/doctor's office if we do not receive a response to our request. We will request the following information: survivorship care plan/treatment summary (if available), dates and types of visits in the past 12 month (i.e., preventive care, survivorship care, or sick visit) and dates and types of medical screening tests/labs completed in the past 12 months.

Measure	Time Point			
	Baseline	Post-Intervention (~8 weeks)	Follow-Up (~5 months)	Follow-Up2 (~12 months)
Readiness for Transition Questionnaire – Survivor Version (RTQ)	x	x	x	x
Transition Readiness Inventory (TRI)	x	x	x	
Fear of Recurrence Scale 	x	x	x	
Perceived public stigma and internalized shame 	x	x	x	
Self-efficacy (general, cancer-survivorship, health insurance, communication)	x	x	x	x
Follow-Up Care Use and Health Outcomes of Cancer Survivors (FOCUS)	x		x	x
Healthcare Practices (i.e., general physical exam, immunizations, dentist, cancer screenings)	x		x	x
Health behaviors (i.e., tobacco, alcohol, exercise, sedentary)	x	x	x	
PROMIS -Self-Efficacy for Managing Chronic Conditions-Managing Emotions -Information Support -Emotional Support	x	x	x	x (Information & Emotional Support only)
Chronic Disease Self-Efficacy: Communicate with physician scale 	x	x	x	x
Working Alliance Inventory – Short Form 		x		
Internet Intervention Utility Questionnaire, Impact Questionnaire, and Adherence Questionnaire.  &		x		

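### Phase 3B mentor ratings are triggered by completion, with no trigger for a pair that ends early or a mentor who withdraws, so they may describe mainly completed pairs

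*Combined protocol and SAP*

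**What the plan says.** The Phase 3B mentor measures are set out in section 4.2, directly after the table of participant measures.

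- **Alliance, rated by the mentor.** "After completing the final call with each mentee, they will be asked to complete" the Working Alliance Inventory for that mentee.
- **Programme ratings by the mentor (Mentor Survey 2).** This is "a survey including program evaluation ratings when they have completed mentoring their last mentee".
- **Other mentor forms.** A self-efficacy survey (Mentor Survey 1) at training, and an evaluation of the training. Neither rates a pairing or the programme as delivered.

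On the participant side, the section 4.2 table places the "Working Alliance Inventory – Short Form" at the post-intervention survey, about 8 weeks after baseline. Section 3.1 says "All participants will be asked to complete surveys at four time points", and does not make this depend on calls.

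Aim 2 (section 1.1) counts among its feasibility measures "reasons for study drop out, and patient and mentor satisfaction with the program".

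The plan gives no fallback date for the mentor forms, no early-termination version, and no rule for a mentor who leaves. It does not say how missing mentor ratings will be handled or which denominator will be reported. The missing-at-random statement in section 5 concerns the multilevel model of transition readiness.

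**The concern.** A feasibility study learns a good deal from the pairings that fail. Here the events that prompt a mentor's rating are those most likely to be absent when a pairing fails. If a mentee stops answering, nobody knows at the time that the previous call was the last, so no form is sent. If a mentor withdraws, the point at which the last mentee is finished may never arrive.

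Two things are at stake. Mentor satisfaction, a named Aim 2 measure, could be summarised largely from mentors and pairs that reached the end. And a comparison of mentor-rated with participant-rated alliance could set two different groups of pairs against each other, because only the mentor side depends on the calls being finished. Ratings not collected at the time cannot reliably be recovered later.

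**Working it through.** The plan states no figure on this point, so there is nothing to reproduce. The check is a comparison of triggers, followed by an illustration.

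**1. Triggers in Phase 3B**

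| Rating | Trigger | If the pair ends early or the mentor leaves |
|---|---|---|
| Mentor alliance | Final call with that mentee | No rule |
| Mentor Survey 2 | Last mentee finished | No rule |
| Participant alliance | Survey at about 8 weeks | Still scheduled |

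In Phase 2, section 4.2 gave mentors and participants the same post-intervention timing for the alliance measure. It also provided an end-of-programme mentor interview, which the Phase 3B list of mentor measures does not mention.

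**2. Number of pairs**

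Section 3.3 gives 50 survivors. The allocation ratio is not stated. Assuming 1:1, there are 50/2 = 25 pairs.

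**3. Mentors for whom one failed pair could remove both ratings**

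Section 3.3 allows up to 20 mentors with up to 5 mentees each. If all 20 take part and each has at least one mentee, there are 25 − 20 = 5 further mentees. At most 5 mentors then have more than one, so at least 15 have exactly one. At the other extreme, 5 mentors with 5 mentees each cover all 25 pairs and none has only one. Section 3.3 expects several mentors to take more than one, so the number lies somewhere between and cannot be fixed.

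**4. Illustration for the alliance mean**

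Let q be the share of pairs without a mentor rating, and d the amount in SD by which those pairs would have rated lower. The mean over all pairs is

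(1 − q) × m + q × (m − d) = m − q × d,

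where m is the mean of the scored pairs. The scored mean is therefore q × d too high. The documents give neither q nor d, so the values below are assumptions.

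| q | Pairs of 25 | d = 0 | d = 0.5 | d = 1.0 | d = −0.5 |
|---|---|---|---|---|---|
| 0.10 | 2.5 | 0 | 0.05 | 0.10 | −0.05 |
| 0.20 | 5 | 0 | 0.10 | 0.20 | −0.10 |
| 0.30 | 7.5 | 0 | 0.15 | 0.30 | −0.15 |

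With no gap there is no distortion. If unscored pairs would rate higher, the sign reverses. For scale, the standard error of a mean over 20 scored pairs is 1/√20 = 0.22 SD if pairs are treated as independent. They are not fully independent, since one mentor may have several mentees.

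The illustration applies to the alliance measure, which is rated per pair. Mentor Survey 2 is completed once per mentor, and the documents give no rate of mentor withdrawal from which to size its loss.

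**The case against.** The other side has substantial points.

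- **A reader might infer that broken pairs are never scored.** The text does not say so. It does not name the sixth call, and the final call could mean the last one held. What stands is that no rule ensures a rating. If the last call held is what the sponsor intends, the plan needs to say so and say who sends the form.
- **A reader might infer that the ratings are biased upward.** That direction is plausible, but neither sign nor size follows from the documents.
- **It is tempting to take 20% to 30% non-retention from Table 1 as the share of failed pairs.** That rule ("40 people complete" the follow-up) counts survey completion among 50 people in both arms. Section 5 defines retention as completing all surveys, and these run to about 12 months. A mentee can finish every call, miss the last survey and still have a mentor rating. The usual-care arm has no mentors. The 30% corresponds to the rate the plan calls unacceptable, so it is not an expectation.
- **A reader might conclude that the trial cannot see poor matches or mentor strain.** It can. Mentors have weekly supervision, calls are recorded and messages archived (section 4.1). Section 5 analyses engagement with the mentor, call completion, barriers and reasons for drop-out. Participants rate alliance at about 8 weeks. These sources do not supply the missing mentor rating, but they do show failing pairs.
- **Mentor Survey 2 is not generally lost when a mentee drops out.** A mentor who loses one mentee and finishes with a later one still reaches it.
- **Little depends on these ratings formally.** Mentor-rated alliance is in no hypothesis, and mentor ratings enter neither the Table 1 rules nor the group comparison of transition readiness.

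These points limit the size and reach of the concern. They do not supply the missing trigger.

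**Conclusion.** The concern holds in a limited form, as a minor point. Both Phase 3B mentor ratings are tied to completion, and nothing prompts them when a pair ends early or a mentor withdraws. Followed as written, the plan tends to select mentor ratings towards completed pairs. The results may then be too favourable, if failed pairs would rate lower, and may not match the pairs covered by the participant-rated alliance.

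The range of 0.05 to 0.30 SD rests on three assumptions: about 25 pairs from 1:1 allocation, 10% to 30% of them unscored, and a gap of 0.5 to 1 SD. It shows what could happen and is not an estimate. The Table 1 feasibility decision does not change under any of these values.

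**What to change.** In the mentor paragraph of section 4.2 (Phase 3B):

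1. Trigger the mentor's alliance rating at the final planned call or, if that call does not take place, at the end of the pairing or about 8 weeks after matching, whichever comes first.
2. Trigger Mentor Survey 2 at the end of the mentor's last pairing or at the mentor's withdrawal.

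In section 5 (Phase 3B), add that alliance ratings are reported against all pairs started and Mentor Survey 2 against all mentors assigned, each split by completed and not completed, with the number missing shown.

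The cost is a change of survey trigger and a few sentences of text. The instruments and staff stay the same, and the weekly supervision contact can carry the request. The downside is that some withdrawn mentors will not reply, so the gap will narrow without closing fully; the stated denominators will make what remains visible. The change needs to be in place before mentoring ends.

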### **4.3 Risk of Harm**

Phase 1: Risks are considered minimal and include breach of confidentiality. Every effort will be made to ensure confidentiality of data.

Phase 2: Risks are considered minimal and include breach of confidentiality. Every effort will be made to ensure confidentiality of data. Peer mentors will be instructed in the importance of maintaining confidentiality and supervised by the PI. Surveys will ask about self-management skills, transition readiness, anxiety, barriers to care, and adherence to follow-up recommendations. Although discomfort related to such questions is unlikely, participants can choose not to answer any question for any reason and may withdraw at any time.

Phase 3A: (same as Phase 1) Risks are considered minimal and include breach of confidentiality. Every effort will be made to ensure confidentiality of data.

Phase 3B: (same as Phase 2) Risks are considered minimal and include breach of confidentiality. Every effort will be made to ensure confidentiality of data. Peer mentors will be instructed in the importance of maintaining confidentiality and supervised by the PI. Surveys will ask about self-management skills, transition readiness, fear of recurrence, self-efficacy, barriers to care, adherence to follow-up recommendations, and health behaviors. Although discomfort related to such questions is unlikely, participants can choose not to answer any question for any reason and may withdraw at any time.

### **4.4 Potential for Benefit**

Phase 1: There is no direct benefit to participants.

Phase 2: There may or may not be a direct benefit to participants. All participants will receive information regarding self-management that may be useful to participants but the study will evaluate the feasibility of implementing the interventions as well as participant-reported satisfaction and relevant quality of life outcomes.

Phase 3A: There is no direct benefit to participants.

Phase 3B: There may or may not be a direct benefit to participants, as we do not yet know if the intervention is better than usual care.

## **5. Data Handling and Statistical Analysis**

Phase 1 (Aim 1):

Data Management: Digital recordings will be transferred off of the recorders to the PI's secure shared drive as soon as possible following the interview and then erased from the recorder.

Transcription will be completed as soon as possible, removing any identifiable information. All transcriptions will be labeled with a subject number rather than any identifiable information.

Digital recordings will be deleted after they are described and checked for accuracy. Paper questionnaires will be labeled with an ID number and stored separately from consent forms in a

**Promoting Follow-Up Care Self-Management for Adolescent and Young Adult (AYA) Childhood Cancer Survivors**

[name], MPH

locked cabinet in the PI's locked office. The key linking subject names and subject numbers will be stored electronically on the PI's password-protected CINJ internal shared drive and destroyed at the end of the study.

**Data Analysis:** Qualitative data will be analyzed using content analysis, following the framework approach described by Pope and colleagues. Specifically, themes will be identified based on the a priori theoretical framework (SMART model). Data will be constantly compared to evaluate fit to the model and new themes that emerge from participants' data will be added to the model. An index of themes will be created and applied systematically to the data using NVivo, a qualitative data analysis software. Data analysis will continue until theme saturation occurred (that is, no new themes emerge from additional participants). Participant feedback on questionnaires will be used to determine if any changes are needed to the outcome measures for Phase 2 of the study.

**Phase 2 (Aims 2 & 3):**

**Data Management:** The Rutgers Cancer Institute of New Jersey has a contract and Business Associate Agreement with TigerText to supply HIPAA-compliant secure messaging services and archiving of messages. TigerText will be used for secure text messaging with participants and between mentors/mentees. TigerText uses AES-256/SSL encryption and exercises a number of physical, technical, and administrative safeguards to protect all messages and data. At the application layer, TigerText uses Secure Socket Layers (SSL) to encrypt all communication between the web browser and the data center, and a processing pipeline that ensures performance and data privacy between customer accounts. TigerText partners with Sonian to archive the messages between participants, which will be used for supervision of mentors and for content analysis to determine how mentors and mentees communicated during the study. The archived message data will be accessed and downloaded by the PI or project coordinator using the secure TigerText web portal and stored electronically on the PI's password-protected CINJ internal shared drive. These data will be labeled with an ID number rather than participant name or other identifier. All interactions in the TigerText system are included in the audit logs to ensure that administrators are properly using the web portal and its services.

Databases for participant recruitment and tracking and participant survey data will be developed in collaboration with the CINJ Population Science Research Support Core using HIPAA-compliant DatStat software. The Core provides access to the DatStat software, facilitates initial study setup, and assists in the event of any technical problem in using the DatStat software.

Approval for use of this software in research studies has been provided by the Rutgers Biomedical and Health Sciences Institutional Review Board (IRB). (The approval process included: obtaining a Technology Professional Service Agreement and a Business Associate Agreement from DatStat; the approval of a Security Questionnaire from the Rutgers Office of Information Technology; and the completion of a Security Risk and Assessment Tool by the Rutgers CINJ Office of Information Technology.) The software allows for research study personnel to be assigned data access and privileges specific to their role on the study. Study team members are given access to the minimum amount of data needed to perform their role on the study.

Online surveys will be completed by participants using a secure website (hosted on DatStat servers). DatStat secure servers are registered with site certificates provided by AddTrust that

## Promoting Follow-Up Care Self-Management for Adolescent and Young Adult (AYA) Childhood Cancer Survivors

[name], MPH

provide for advanced encryption over the wire. As each user moves through the survey form, his/her responses are encrypted while in-transit between the browser and DatStat's server using SSL (Secure Sockets Layer) and 40, 56, or 128-bit Public Key Encryption. All servers used for data collection are highly fault-tolerant and equipped with redundant, hot-pluggable power supplies, redundant network interfaces, and RAID 5 hot-swappable disk storage. All primary servers are plugged into a monitored, uninterruptible power supply (UPS). DatStat servers are stored in a locked server cabinet/rack, which are housed in a state-of-the-art, well-ventilated data center. Physical access to servers and data backup is restricted to a minimal number of information technology professionals. The servers are secured with physical and firewall security.

Participants will complete surveys online or via paper (depending on participants' choice). Paper surveys will be identified using only a subject number and will be entered into the database by study staff and kept in a locked filing cabinet accessible only by authorized study staff. We will keep a separate electronic key linking codes and subject names on the PI's department drive. This key will be destroyed at the end of the study. De-identified data will be kept indefinitely. Audio files of video/phone calls between peer mentors and mentees will be recorded using the peer mentor's handheld audio recorder. The peer mentor will then use Rutgers Large File Transfer Service (LiFT) to securely upload the files for the study team to review. This service allows both internal and external users to upload files securely with their email and password. The peer mentors will be instructed to destroy the files after they have successfully uploaded files to Rutgers LiFT for study team to review. Peer mentors will receive training on how to securely transfer the files and delete the files from their devices during the mandatory in-person peer mentor training. The study team will download the files via the secure LiFT service and store them on the Rutgers secure shared drive accessed via a password-protected computer. For participant exit interviews, study staff will record the interview, transfer to the secure shared drive (access limited to pertinent research team members). Recordings will be transcribed as soon as possible, removing any identifying information from the written document. Recordings will be destroyed upon completion of the study procedures.

**Data Analysis:** We will examine feasibility through study enrollment rates, retention rates, reasons for study drop out, adherence to the intervention, and patient and mentor satisfaction with the program. Descriptive analyses (frequencies, means) will be used to evaluate our hypotheses regarding expected enrollment (>50%), retention (>75%), and completion of intervention sessions (>75%). We based these predictions using the literature describing barriers to recruiting AYA participants and the team's collective experience in intervention development and implementation.

To assess the preliminary outcomes of the peer mentor self-management program, we will evaluate whether participants in the program demonstrate improvement in transition readiness and the impact of cancer, and reductions in symptoms of depression and anxiety. We will also explore adherence outcomes. We will compare scores on outcome measures at the end of 6-week assessment using dependent/paired t-tests. Since the primary purpose of this project is to evaluate feasibility, we recognize that we do not have adequate power to detect small to medium statistical effects. Exit interviews will be reviewed to identify strengths of the intervention, weaknesses of the intervention, and ideas to improve the intervention.

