### **3.3 Sample Size Justification**

Phase 1: Total sample size is 24-28, including 10 AYA survivors, 10 parents of AYA survivors, and 4-8 physicians who work with AYA survivors. Qualitative data will be analyzed on a continuing basis. Pooling data across participants, we expect 24-28 interviews will be adequate to achieve data saturation (that is, no new themes emerge from additional participants).

Phase 2: 40 AYA survivors and 20 peer mentors will be recruited for the pilot trial to evaluate feasibility (primary objective) and preliminary outcomes (secondary objective). As this is a feasibility study, we recognize we are underpowered to detect small or medium effects. Published data suggest 5-9% of survivors are African American or Hispanic; data from the NJSCR show greater diversity, with 11.6% of patients diagnosed with cancer at age 10-19 during the period of 2008-2012 reporting as African American, 19% reporting as Hispanic, and 5.7% as Asian American/Pacific Islander. We will oversample these groups.

Phase 3A: Up to 20 AYA survivors will be recruited for usability testing of the online intervention. Given the preliminary work conducted in Phase 2, we expect 12-20 sessions will achieve data saturation (i.e., no new issues emerge according to pre-specified stopping criteria). Usability testing is designed to be iterative in that changes can be made to the site after a small number of participants. Therefore, participants who agree may be asked to complete multiple usability sessions over the course of a few months to provide additional feedback on changes or new features added. Thus we expect about 12 to 20 participants will be needed to achieve data saturation.

Phase 3B: Total sample size is 50 AYA survivors. We chose the sample size and decision rules so that the probability of declaring feasibility would be approximately 5% under unacceptable rates of acceptance/completion and exceed 95% under acceptable rates. If true acceptance and completion rates were 41% and 70%, respectively, which we consider too low to move to an efficacy trial, then the probability of declaring feasibility would be 5%.

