### Phase 3B:

**Data Management:** The same procedures used in Phase 2 will be used in Phase 3B, with the exception that TigerConnect (previously called TigerText) will be used for secure messaging as well as secure videoconferencing (instead of doxy.me). Additionally, TigerConnect now allows for secure file transfer so that peer mentors can securely transfer audio recordings to the study team either via Rutgers LiFT or TigerConnect. For participants who consent to be contacted for future studies, the study team will store their contact information separately from research records on the PI's secure One Drive, with access granted only to the PI, study coordinator, and limited authorized research staff. We will store this information for up to 10 years from date of consent.

We will utilize HIPAA compliant Qualtrics survey tool to request the name and contact information of the physician they have seen in the past 12 months to understand their health care utilization during the study period and to obtain their electronic signature on the Release of Medical Record form. Any paper copies will be kept in a locked filing cabinet in the PI's office.

**Data Analysis:** We will examine feasibility through study enrollment rates, retention rates, usability/engagement with online modules and peer mentor, barriers to engagement, and reasons for study drop out. Descriptive analyses (frequencies, means, confidence intervals) will be used to evaluate hypotheses regarding enrollment ( $>50\%$ ), retention ( $>80\%$  complete all surveys), and intervention completion ( $>75\%$  modules/mentor calls). Multilevel modeling (MLM) will be used to examine differences between the intervention and usual care groups over time on transition readiness (RTQ Adolescent Responsibility and TRI total scores). Our primary analysis will consider both time and treatment to be categorical with an interaction between the two. The interaction will be assessed to determine whether change in transition readiness differs between the two groups. The MLM approach assumes any missing observations are missing at random but includes all observed data. Exploratory analyses of additional outcomes (e.g., self-efficacy, adherence to medical appointments and screenings, and health behaviors) will use the identity link or the logit link as appropriate for continuous or binary outcomes.

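### Phase 2 retention has two benchmarks, >80% in Hypothesis 1 and >75% in the Phase 2 analysis; they should be reconciled, though the effect is confined to how Phase 2 feasibility is reported

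*Combined protocol and SAP*

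**What the plan says.** Section 1.1, Aim 2, Hypothesis 1 gives the expectation "we expect enrollment >50% of eligible patients and retention >80" percent. Hypothesis 2, under the same aim, expects more than 75% of intervention sessions to be completed. Neither names a phase, whereas Hypotheses 3 to 5 under Aim 3 are each labelled Phase 2 or Phase 3.

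The Phase 2 part of section 5 is headed "Phase 2 (Aims 2 & 3"), so it covers Aim 2. Its Data Analysis paragraph says: "Descriptive analyses (frequencies, means) will be used to evaluate our hypotheses regarding expected enrollment", and the list of figures reads "expected enrollment (>50%), retention (>75%), and completion of intervention sessions (>75" percent.

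Section 3.3 makes feasibility the leading purpose of Phase 2: "40 AYA survivors and 20 peer mentors will be recruited for the pilot trial to evaluate feasibility (primary objective").

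The Phase 3B Data Analysis uses more than 80% for retention and ties it to survey completion ("complete all surveys), and intervention completion"). Table 1, also for Phase 3B, lists 80% as the acceptable retention rate.

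**The concern.** The Phase 2 analysis presents itself as an evaluation of hypotheses already stated, not as the place where a new criterion is set. The only retention hypothesis in the document is the one under Aim 2, and its figure is five percentage points higher. A reader following the plan literally therefore has two benchmarks for one of the numerical expectations attached to the primary objective of Phase 2.

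At some results the same count could be reported as meeting the expectation or as falling short, and nothing in the plan stops the more lenient figure from being chosen once the data are known.

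**Working it through.** **Inputs**
- Benchmark A: retention >80% (section 1.1, Aim 2, Hypothesis 1).
- Benchmark B: retention >75% (section 5, Phase 2 Data Analysis).
- Denominator: 40 survivors (section 3.3, Phase 2), assuming full enrollment and leaving out the 20 mentors.
- True retention rates: the documents give none for Phase 2, so 70% to 90% is assumed for illustration.

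The plan derives no sample size, power or error rate from Phase 2 retention, so there is no stated figure to reproduce.

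**Side by side**

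| Item | Aim 2 hypotheses | Phase 2 analysis | Phase 3B analysis |
|---|---|---|---|
| Enrollment | >50% | >50% | >50% |
| Retention | >80% | >75% | >80% |
| Session completion | >75% | >75% | >75% |

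Only one cell is out of line.

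**Counts that separate the benchmarks**
- 0.75 × 40 = 30, so strictly more than 75% needs at least 31.
- 0.80 × 40 = 32, so strictly more than 80% needs at least 33.
- 30/40 = 75.0% misses both. 31/40 = 77.5% and 32/40 = 80.0% meet B and miss A. 33/40 = 82.5% meets both.

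If both signs were read as at least, the split would fall at 30 and 31 instead.

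**Chance of landing on 31 or 32**

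With X ~ Binomial(40, p), P(X = 31 or 32) = P(X ≥ 31) − P(X ≥ 33).

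| Assumed true p | P(X ≥ 31) | P(X ≥ 33) | P(31 or 32) |
|---|---|---|---|
| 70% | 0.196 | 0.055 | 0.141 |
| 75% | 0.440 | 0.182 | 0.258 |
| 80% | 0.732 | 0.437 | 0.295 |
| 85% | 0.933 | 0.756 | 0.177 |
| 90% | 0.995 | 0.958 | 0.037 |

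The chance peaks at about 30%, near a true rate of 79%. The values at 75% and 80% are thus close to the worst case.

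**What the data could distinguish**

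The Wilson 95% interval is [p̂ + z²/2n ± z√(p̂(1−p̂)/n + z²/4n²)] / (1 + z²/n), with n = 40 and z = 1.96. For 31/40 it is (0.775 + 0.048 ± 0.138)/1.096, or 62% to 88%. For 32/40 it is (0.800 + 0.048 ± 0.133)/1.096, or 65% to 90%. Each interval contains both 75% and 80%, so at the disputed counts the interval says more than either verdict.

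**The case against.** The strongest reply is that nothing turns on the number. Phase 2 is a single-arm pilot assessed by frequencies and means, and for outcome effects the protocol itself says: "As this is a feasibility study, we recognize we are underpowered to detect small or medium effects". Sections 1 and 3 carry the program into Phase 3 without any retention condition, and the formal feasibility rules in Table 1 belong to Phase 3B. This stands. A reader might infer that the discrepancy puts the decision to proceed, or the randomized trial, in doubt; the documents do not support that. For the same reason the binomial figures describe how often two reports would disagree, not the error rate of a decision rule.

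A second reply is that 75% may have been a deliberate Phase 2 figure. That paragraph is the phase-specific one and attributes its predictions to literature and team experience. This stands in part. The attribution covers all three figures and does not say why retention alone should depart from Aim 2, but the documents do not prove which number was intended. It would go too far to call 75% simply a mistake.

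Third, the current text (Version 3, dated 12.13.2020) suggests that Phase 2 is over: it refers to work already conducted in Phase 2 and to doing things as they were done then. No completion date is given, so this is inference. If it is right, editing the threshold now would itself be a change of criterion after the data. This stands and shapes the fix.

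Finally, Phase 2 retention is not defined. Reading it as completion of the survey at about 6 weeks is natural, since measures are taken at baseline and then, but only Phase 3B defines retention by surveys. The contradiction does not depend on this definition; the particular counts do.

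**Conclusion.** The inconsistency is real and unexplained: two retention benchmarks apply to Phase 2, and with 40 survivors and strict inequalities they give opposite readings at 31 or 32 retained. The chance of that ranges from about 4% to 29% over the assumed true rates tabulated. It rests on full enrollment of 40, on the literal strict sign, and on retention being a simple count of survivors.

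The severity is minor. What is affected is whether one Phase 2 feasibility expectation is reported as met. A reader might also take this for a miscalculation, but no computation in the plan is wrong; two statements disagree. More than 80% is the better-supported figure, as the only stated retention hypothesis and the one repeated in Phase 3B, without being shown to be the intended one.

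**What to change.** Bring section 1.1 (Hypothesis 1) and section 5 (Phase 2 Data Analysis) to a single retention threshold, and say in a few words what counts as retained in Phase 2 and over which denominator. The default should be >80%. If the sponsor can document that >75% was the Phase 2 criterion in force before any Phase 2 data were seen, keep it and add a phase label to Hypothesis 1 so that the two no longer conflict.

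If Phase 2 is already complete, do not alter the criterion retroactively. Report the observed retention with its confidence interval, set it against both 75% and 80%, and disclose that the protocol carried both figures.

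The cost is one number and a clarifying sentence, or one sentence in the report. Sample size, conduct and the Phase 3B rules are unchanged. If >80% is adopted prospectively, the Phase 2 expectation becomes harder to meet by two participants (33 rather than 31 of 40).
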